1.9.2 Benefits

This is the first clinical trial with the CyPep-1 injectable solution. The principal aim of this trial is to obtain safety and preliminary efficacy data when CyPep-1 is intratumorally administered to subjects with solid tumors for whom no other treatment options currently exist, as monotherapy and in combination with pembrolizumab. In addition to the minimal risk using the starting dose of 0.5 mg/mL of CyPep-1, preclinical experience as well as the safety profile of cohort 1 with the compound indicate a potential benefit that might be expected in terms of clinical efficacy. Preclinical assays describing the synergy of CyPep-1 with anti-PD-1 antibody treatment indicates the potential benefit of this therapeutic combination in patients with cancer.

The safety and efficacy data, together with the pharmacokinetic and pharmacodynamic data obtained from this trial, will help establish the treatment regimen and recommended doses suitable for subsequent clinical trials in the target population. Treatment of subjects with CyPep-1, as monotherapy and in combination with pembrolizumab, is hypothesized to result in improvement or stabilization of the disease state of the subjects.

1.9.3 Management of Risks

To minimize the risk to subjects and maximise safety, the following factors have been incorporated into the study design. Detailed safety and laboratory assessments will be performed.

- All clinical observations will be evaluated by the investigator on an ongoing basis.
- Each subject must stay on site for at least 4 hours after study drug administration on each treatment day (vital signs will be assessed on each treatment day pre-dose and at 15 minutes, 30 minutes, and 1, 2, and 4 hours post-dose during the first treatment cycle and on Day 1 of each additional treatment cycle). If only pembrolizumab is administered, subjects are not required to stay at the site for 4 hours for vital signs assessments. For Arm D, for subjects who have no clinically significant abnormal vital signs reported during the first four doses of CyPep-1 (in Week 1 to 4), the post-dosing safety monitoring at the clinic can be shortened to 1 h on all the subsequent dosing days.
- Premedication is mandatory prior to the first IT dose of CyPep-1. Premedication is started 30-60 minutes before the IT injection, and continues for up to 24-48 hours after the procedure was completed, if necessary. An antihistamine (e.g., 25 to 50 mg clemastine) is mandatory with optional anxiolytics if deemed appropriate by the investigator. Only for subjects experience pain during or after IT administration, it is recommended to provide celecoxib 400 mg as premedication every 6 hours for 24-48 hours. Premedication should be administered for subsequent CyPep-1 doses based upon clinical judgment and presence/severity of prior reactions. This regimen may be modified based on local treatment standards and guidelines as appropriate.
- For all subjects in Phase I, the first 3 subjects in Arm B, and the subjects in Arm C cohort 4, there must be a window of at least 24 hours between each subject's treatment start. This is not applicable for the subjects in Phase IIa Arm A, remaining subjects in Arm B, Arm C cohort 5, and Arm D.
- CyPep-1 will not be administered if at the time of the planned administration the subject is suffering from severe infection or receiving steroid-based immunosuppressive therapy (excluding topical steroids).
- The study agent must be administered in a clinical setting where emergency resuscitative equipment and personnel trained in the management of anaphylaxis are

immediately available to treat systemic reactions under the direct supervision of a physician.

To minimize the risks to subjects upon administration of pembrolizumab, the following measures are recommended, depending on the situation ([Sections 5.3.6.2](#) and [5.3.6.3](#) for complete list of considerations on dose modification of pembrolizumab based on the occurrence and severity of immune- or infusion-related AEs):

- Suspected Stevens-Johnson syndrome or toxic epidermal necrolysis: withhold until recovery to Grades 0-1; if this does not occur within 12 weeks after last dose of pembrolizumab or if corticosteroid dosing cannot be reduced to ≤ 10 mg prednisone or equivalent per day within 12 weeks, pembrolizumab should be permanently discontinued.
- Confirmed Stevens-Johnson syndrome or toxic epidermal necrolysis: permanent drug discontinuation.
- Grade 3 or 4 myocarditis, encephalitis, or Guillain-Barre syndrome: withhold until recovery to Grades 0-1 or, if above conditions apply, permanently discontinue.

Phase IIa Arm B:

CyPep-1 monotherapy can continue if there is unacceptable toxicity to pembrolizumab. Pembrolizumab monotherapy can continue if there is unacceptable toxicity to CyPep-1. Related dose modification rules for CyPep-1 and pembrolizumab is detailed in [Section 5.3.6](#)).

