In three dose cohorts of 3 subjects each, subjects will receive CyPep-1 IT at different concentrations (dose escalation) and volumes (depending on tumor size), i.e., 0.5 mg/mL, 2 mg/mL, or 5 mg/mL, respectively. These dose concentrations have been selected based on previous pre-clinical experience with CyPep-1.

Each subject will receive IT injection(s) with CyPep-1 on Day 1 of Weeks 1, 3, and 5, respectively. After each CyPep-1 administration, subjects will be required to stay at the clinic for at least 4 hours for safety and, for those in which PK will be assessed, also for PK monitoring. The data from the additional three subjects in cohort 3 will be used for further confirmation of RP2D. The following CyPep-1 administrations are planned as continuous Q2W administrations.

For each dose cohort, at least 24 hours must elapse between each subject to start treatment with CyPep-1. No intra-subject dose escalation is allowed.

The decisions on dose escalation and MTD will be taken by the Dose Escalation Committee (DEC) after reviewing safety data (including DLTs) from all subjects who have entered the

previous dose cohort and have completed the DLT observation period. The DEC is comprised of all the investigators or designees, as well as the medical monitor and representatives of the sponsor.

In Phase I, subject replacement for subjects who drop out for any reason, except DLTs, will only occur before the DLT observation period is completed and is allowed if a subject does not receive all three CyPep-1 administrations, unless due to CyPep-1-related toxicity. No subject replacement will occur for subjects who withdraw later.

After completion of Phase I, all results will be evaluated by the DEC. This will include safety data and if available, other supportive clinical data (i.e., efficacy, pharmacokinetics, tumor biopsy analyses) from all subjects included in Phase I of the trial. The DEC will confirm the MTD or RP2D (in case the MTD is not reached).

All additional arms can start once Phase I data has been evaluated by the DEC and an RP2D is determined for CyPep-1.

Phase I has been completed in August 2021 and the RP2D of CyPep-1 was determined at 5 mg/mL.

Phase IIa – dose expansion (Arm A):

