In this phase, safety and tolerability will be further evaluated in an expanded cohort of 9 subjects at the RP2D of CyPep-1, determined in Phase I. Screening- and treatment-schedules will be the same as in Phase I, except for the 24-h observation period before start of treatment of the next subject, which is not applicable.

At the RP2D, in case of a responder per iRECIST or of 2 subjects with stable disease per iRECIST, the number of subjects will be expanded to a total of 18 (to evaluate overall data from a total of 24 subjects treated at RP2D for CyPep-1 monotherapy taking the 6 subjects from cohort 3 into account).

Replacement of subjects in the Phase IIa expansion monotherapy arms is not planned.

Phase IIa – combination arm (Arm B):

The safety and tolerability of CyPep-1 in combination with pembrolizumab will be evaluated in a cohort of 15 subjects in total, using a staggered approach. Initially, 3 subjects will receive CyPep-1 at RP2D in combination with pembrolizumab Q6W and each subject will be observed for 24 h before the next subject can be administered with CyPep-1. After the first 3 subjects completed the TLT observation period of 6 weeks with no TLTs observed and after reviewing the safety data (including TLTs) by the DEC, the inclusion of all remaining subjects at RP2D of CyPep-1 in combination with pembrolizumab can be initiated. In the absence of any TLTs in the initial 3 subjects, the 24-h observation period before start of treatment of the next subject is no longer applicable. Should any TLTs be observed in the first 3 subjects at the RP2D of CyPep-1 in combination with pembrolizumab, an additional 3 subjects in this dose group will be included. If ≤1 out of 6 subjects have a TLT, the remainder of the 15 subjects will be treated at the RP2D. In the unlikely case that 2 or more of the 6 subjects experience any TLTs at RP2D of CyPep-1, a recommendation to dose de-escalate CyPep-1 and to what dose or to continue the combination part of the trial will be made by the DEC. The same screening schedule is planned and CyPep-1 will be administered according to the same treatment schedule as in Phase I.

For arm B, replacement of the first three subjects is allowed if a subject drops out for any reason, and does not receive all three CyPep-1 injections during the TLT observation period, unless due to CyPep-1- and/or pembrolizumab-related toxicity. No subject replacement will occur for subjects who discontinue later.

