Phase IIa – dose expansion liver metastases (Arm C):

The safety and tolerability of at least two dose levels of CyPep-1, the RP2D and the dose immediately below that, are planned to be evaluated when CyPep-1 is administered intratumorally using ultrasound guidance to one metastatic lesion in the liver. The two dose levels are planned to be investigated adhering to the “3+3” design and will follow the procedures as described for the dose escalation (Phase I) (Section 3.1). The first three subjects will receive CyPep-1 at the lower dose level and each subject will be observed for 24 h before CyPep-1 administration to a next subject (cohort 4). After the third subject at that dose finished the DLT observation period of 6 weeks (5 weeks CyPep-1 treatment plus 1 week safety follow-up), the DEC will recommend on the start of the cohort to be administered at RP2D based on the review of the safety data (cohort 5). After the DLT observation period for the first three subjects at RP2D for CyPep-1 and the review of all safety data, the DEC will recommend on the inclusion of all remaining subjects. In the absence of any DLTs in the first 3 subjects, the 24-h observation period before start treatment of the next subject is not applicable. Should a DLT be observed in the first three subjects at the RP2D of CyPep-1, an additional three subjects in this dose group will be included. In case that two or more subjects experience DLTs at RP2D of CyPep-1, a decision to dose de-escalate and to what dose and how to continue Arm C will be made by the DEC.

For Arm C, replacement for subjects who drop out for any reason, except DLTs, before the DLT observation period is completed is allowed when a subject did not receive all three CyPep-1 administrations. No subject replacement will occur for subjects who discontinue later.

Phase IIa – dose expansion melanoma (Arm D):

The safety and tolerability of CyPep-1 at RP2D will be further evaluated with focus on assessing efficacy signals of CyPep-1 monotherapy in up to 30 subjects with melanoma. Although safety information will be collected, there will not be a formal DLT observation period.

As part of the continuous safety monitoring of the trial, reports with cumulative safety data of Arm D subjects will be shared with all investigators, competent authorities, and ethical committees of countries where the trial is conducted at the following time points:

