In case in the first 12 subjects at RP2D, a responder per iRECIST (ORR as CR/PR as best response) or 2 subjects with stable disease (SD with duration >16 weeks from onset) per iRECIST are observed, the number of subjects will be expanded to a total of 24 (CyPep-1 monotherapy; subjects cohort 3 of Phase I and in Phase IIa Arm A).

Phase IIa – combination arm (Arm B):

The safety and tolerability of CyPep-1 in combination with pembrolizumab will be evaluated in a cohort of 15 subjects in total, using a staggered approach. Initially, 3 subjects will receive CyPep-1 at RP2D in combination with pembrolizumab and each subject will be observed for 24 h before the next subject can be administered with CyPep-1. After the first 3 subjects completed the TLT observation period of 6 weeks with no TLTs observed and after reviewing the safety data (including TLTs) by the DEC, the inclusion of all remaining subjects at RP2D of CyPep-1 in combination with pembrolizumab can be initiated. In the absence of any TLTs, the 24-h observation period before start treatment of the next subject is no longer applicable. Should any TLTs be observed in the first 3 subjects at the RP2D of CyPep-1 in combination with pembrolizumab, an additional 3 subjects will be included in this dose group. If ≤1 out of 6 subjects have a TLT, the remainder of the 15 subjects will be treated at the RP2D. In the unlikely case that 2 or more of the 6 subjects experience any TLTs at RP2D of CyPep-1, a recommendation to dose de-escalate and to what dose or to continue the combination part of the trial will be made by the DEC. The same screening is planned, and CyPep-1 will be administered according to the same schedule as in Phase I.

Scheduling of treatment of CyPep-1 and pembrolizumab (Arm B) will be as follows: CyPep-1 will be administered every 2 weeks (Q2W) and pembrolizumab will be administered following a Q6W schedule starting on Day 1, as per standard of care. Radiological assessment to determine occurrence of (un)confirmed PD will be performed Q8W from the start of treatment. Treatment will continue until confirmed PD, unacceptable toxicity or consent withdrawal, loss to follow up, or trial end, whichever occurs first.

Phase IIa – dose expansion liver metastases (Arm C):

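### Section 1.9.3 drops the no-TLT and no-DLT conditions that the design text puts on lifting the 24-hour stagger in Arm B and Arm C cohort 5, and the protocol never says when the Arm B gap ends after a TLT

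*Protocol*

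**What the plan says.** **Section 1.9.3, Management of Risks.** The requirement covers three groups: "For all subjects in Phase I, the first 3 subjects in Arm B, and the subjects in Arm C cohort 4, there must be" a gap of at least 24 hours between treatment starts. The exemption follows: "This is not applicable for the subjects in Phase IIa Arm A, remaining subjects in Arm B, Arm C cohort 5, and Arm D". Neither sentence mentions toxicity.

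**Arm B design text.** The synopsis and SAP 6.1 make the waiver conditional: "In the absence of any TLTs in the initial 3 subjects, the 24-h observation period before start of treatment" of the next subject is lifted. Section 3.1 is similar: "In the absence of any TLTs, the 24-h observation period before start treatment of the next subject is no longer applicable". The toxicity branch comes next: "Should any TLTs be observed in the first 3 subjects at the RP2D of CyPep-1 in combination with pembrolizumab, an additional 3 subjects" are enrolled at the same dose. If no more than 1 of the 6 has a TLT, "the remainder of the 15 subjects will be treated at the RP2D".

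**Arm C design text.** Both dose levels "will follow the procedures as described for the dose escalation (Phase I"), and the Phase I rule reads: "For each dose cohort, at least 24 hours must elapse between each subject to start treatment with CyPep-1". The only 24-hour instruction written specifically for Arm C is tagged to cohort 4 (2 mg/mL). A further sentence lifts the gap if the first 3 subjects have no DLTs. In the synopsis and SAP 6.1 it follows the review of the first three subjects at the RP2D (cohort 5, 5 mg/mL). In Section 3.1 it comes earlier, straight after the decision to open cohort 5 on the cohort 4 data.

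**The concern.** Section 1.9.3 is the protocol's own list of measures built in to minimise risk, so a site may reasonably work from it. In Arm B, the 3 added subjects are enrolled because a TLT was seen. The design text's condition for lifting the gap is then not met, yet Section 1.9.3 does not require the gap. Two sites could act differently, each citing the protocol, and Section 10.7 counts any non-compliance with the protocol as a deviation.

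What is at stake is narrow. A 24-hour gap helps only if an acute reaction appears before the next subject is dosed. Section 1.9.1 names allergic reaction as a potential risk, so the gap has a purpose. Several TLT criteria, such as a delay of more than 2 weeks in starting Cycle 2, cannot be seen within 24 hours.

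**Working it through.** The documents give no figure on this point, so there is none to reproduce. The check is a comparison of texts, followed by arithmetic for scale.

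**Arm B**

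| Situation | Synopsis, Section 3.1, SAP 6.1 | Section 1.9.3 | Result |
|---|---|---|---|
| No TLT in first 3 | Gap lifted | Gap not applicable to remaining subjects | Agree |
| TLT in first 3; subjects 4 to 6 | Waiver condition unmet; gap continues by implication | Gap not required | Condition dropped |
| At most 1 TLT in 6; subjects 7 to 15 | No end of gap stated | Gap not applicable | Unresolved |

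The second row does not depend on who the remaining Arm B subjects are. If they are subjects 4 to 15, the added 3 are exempted. If they are only those enrolled after a clean first 3, the added 3 are not mentioned. Either way Section 1.9.3 does not require the gap for them.

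**Arm C, cohort 5**

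| Reading of the waiver sentence | Design text for cohort 5 | Section 1.9.3 | Result |
|---|---|---|---|
| Synopsis/SAP order: first 3 at RP2D | First 3 staggered through the inherited Phase I rule; 3 more after a DLT | Exempt | Conflict |
| Section 3.1 order: first 3 of cohort 4, no DLT | Gap lifted | Exempt | Agree |
| Section 3.1 order: 1 DLT in first 3 of cohort 4, 0 in next 3 | Condition unmet | Exempt | Condition dropped |

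The third row can occur because the 3+3 table in Section 3.1 allows escalation after 1 DLT in 6. Cohort 4 itself is unaffected: Section 1.9.3 requires the gap for all of it.

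**Scale.** No TLT or DLT rate is given, so p is assumed at 0.05, 0.10 and 0.20 per subject, with subjects independent.

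- Any TLT in 3 = 1 − (1 − p)³: 1 − 0.857 = 0.143; 1 − 0.729 = 0.271; 1 − 0.512 = 0.488.
- One TLT in the first 3 and none in the added 3, so that Arm B continues under the 1-in-6 rule = 3p(1 − p)⁵: 0.15 × 0.774 = 0.116; 0.30 × 0.590 = 0.177; 0.60 × 0.328 = 0.197. In these cases subjects 7 to 15 also have no stated end to the gap.
- Cohort 5 opens = (1 − p)³ + 3p(1 − p)⁵: 0.973; 0.906; 0.709. Share of these openings that follow a cohort 4 DLT: 0.116/0.973 = 0.119; 0.177/0.906 = 0.195; 0.197/0.709 = 0.277.
- Section 5.3.4 reports no DLTs at 5 mg/mL, and the synopsis puts 6 subjects in Phase I cohort 3. The exact one-sided 95% upper bound for 0/6 is 1 − 0.05^(1/6) = 0.393. Those data are for monotherapy, so they neither exclude the assumed rates nor inform the combination.

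**Time.** Three added subjects have 2 gaps, at least 2 days. If the gap never ended after a TLT, subjects 4 to 15 (12 subjects) would have 11 gaps, at least 11 days.

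**The case against.** The strongest reply is that Section 1.9.3 is a summary in the Introduction and Section 3.1 is the operative text. The design text speaks of all remaining subjects when it means those enrolled after a clean first 3, and treats the added 3 separately. Read that way, Section 1.9.3 describes the clean path and is silent on the TLT branch. Moreover, no sentence states outright that the gap continues after a TLT; this is inferred from the wording of the waiver.

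This stands in part. A reader might infer that Section 1.9.3 forbids staggering the added 3. The documents do not go that far: it can be read as merely silent. But silence in the risk-management list, where the design text sets a condition, is still a gap, and the inference is the natural one: a gap that always ended after subject 3 would need no TLT condition.

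On Arm C the reply is stronger. A reader might infer that the protocol requires a stagger for the first 3 cohort 5 subjects and that Section 1.9.3 contradicts it. The documents do not establish that. The only explicit Arm C gap is tagged to cohort 4, and the Section 3.1 sentence order, together with Section 1.9.3 itself, supports reading the waiver as referring to cohort 4. A cohort 5 stagger rests on the general clause importing Phase I procedures and on the sentence order in the synopsis and SAP.

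The practical weight is also limited. Premedication, 4-hour observation, anaphylaxis cover and DEC review all remain, and the DEC includes all investigators or their designees.

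**Conclusion.** The point holds as an inconsistency in a safety instruction, with a small practical effect.

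- **Arm B.** Section 1.9.3 omits the condition for lifting the gap, and no text gives its end after a TLT. This concerns subjects 4 to 6 of 15, if a TLT occurs in the first 3: 14%, 27% or 49% at assumed rates of 5%, 10% or 20%. These are chances that the question arises, not chances of harm.
- **Arm C.** The unconditional exemption of cohort 5 drops a condition on either reading, but how often this matters depends on the reading. On the Section 3.1 order, it matters only when cohort 5 opens after a cohort 4 DLT: 12%, 20% or 28% of openings at the same assumed rates. On the synopsis order, it affects the first 3 cohort 5 subjects of the 9 planned in Arm C, and 3 more after a DLT. They may receive up to 4 mL × 5 mg/mL = 20 mg in one liver lesion, against 4 mL × 2 mg/mL = 8 mg in cohort 4. The documents do not settle which reading is meant.

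A reader might also infer that the trial's safety conclusions are weakened. Nothing supports that: no analysis set, endpoint, sample size or estimate depends on the stagger.

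**What to change.** **Arm B.** In Section 1.9.3, state that the 24-hour gap applies to the first 3 subjects and, if any of them has a TLT, also to the 3 added subjects, and that it ends once the DEC has reviewed those 6 and allowed enrolment to continue. Put the same sentence in the Arm B text of the synopsis and Section 3.1, so that the operative text also carries the end point. Amend SAP 6.1 for consistency only. The end rule is a proposal, since the documents contain none; the sponsor may choose another, provided it is stated.

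**Arm C.** In the synopsis and Section 3.1, name the cohort whose first 3 subjects are meant and use one sentence order, with SAP 6.1 aligned. In Section 1.9.3, make the cohort 5 exemption conditional on no DLT in that group. A stagger for the first 3 cohort 5 subjects should be written in only if the sponsor intends the synopsis reading.

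The documents do not give enrolment status for Arms B and C. If the affected subjects have already been dosed, the sponsor should record which rule was applied.

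**Cost.** A few sentences, and at least 2 days per added group of 3, incurred only after a TLT or DLT. If the sponsor adopts the synopsis reading, the first 3 of cohort 5 also take at least 2 days. The stated end point saves time against a literal reading of the present Arm B text: at least 2 days rather than at least 11.

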24. Continuous Q2W CyPep-1 treatment is planned and until confirmed PD, unacceptable toxicity or consent withdrawal, loss to follow up, or trial end, whichever occurs first. Lesions not originally planned to be injected with CyPep-1 at screening may also be injected per investigator's discretion, if necessary and after consulting with medical monitor. Follow-up visits will follow the interval as defined in **Table 1a/c**. For subjects in the combination arm treatment with pembrolizumab will continue as per SoC following Q6W dosing until PD, unacceptable toxicity or consent withdrawal.

25. Per additional cycles: C2, C3, ...Cn. CXV1 is scheduled 2 weeks after the last CyPep-1 administration (to follow a Q2W administration schedule).

26. If a subject is receiving additional Q2W treatment with CyPep-1, a biopsy of any new injected lesion(s) can be taken (not mandatory) after 6 weeks for each subsequent cycle. A biopsy at CxD1 (pre-dose) is only applicable if any new lesion(s) are selected for CyPep-1 injection (not mandatory). Arrangements to be made for any tumor material to be sent for analysis are described in the laboratory manual. The visit window for biopsies on CxV4 is ± 3 days.

27. Cytokine levels should only be assessed in the first and second cycles of CyPep-1 administration.

28. The visit window for biopsies on C1V4 is ± 3 days.

29. Pembrolizumab administration only in the combination arm (Arm B). Pembrolizumab should be administered as per SOC Q6W independent of other administrations or assessments (see **Section 5.3.2** for details regarding pembrolizumab administration). CyPep-1 should be administered 30 to 60 min after pembrolizumab if on the same day. All safety assessments and safety laboratory testing should be performed on all pembrolizumab administration days as specified in **Table 1c**. Pembrolizumab will be administered using IV infusion after all procedures and assessments have been completed. See **Section 5.3.6.2** for dose modifications and toxicity management. Pembrolizumab will be administered to a maximum of 18 cycles and then stopped.

30. Thyroid panel should include: triiodothyronine (T3) or free triiodothyronine (FT3); free thyroxine (FT4); thyroid stimulating hormone (TSH).

31. The frequency for tumor biopsy is every 6 weeks from D1 if a subject stays on treatment. The biopsy of at least one injected lesion is highly desired but not mandatory.

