- Completion of 18 (for Q6W dosing) administrations (approximately 2 years) with pembrolizumab

(Note: The number of administrations is calculated starting with the first dose of pembrolizumab.)

- Any study intervention-related toxicity specified as a reason for permanent discontinuation as defined in the guidelines for dose modification due to AEs in Section 5.3.6. If CyPep-1 treatment is delayed > 7 days, that dose will be omitted. If the delay of > 7 days is during the TLT observation period, the subject will be replaced.

For Phase I, Phase IIa Arms A and C, if CyPep-1 treatment is delayed for > 6 weeks during the DLT period (first 3 injections), the subject should be discontinued from the trial. For Arm B, treatment with pembrolizumab may continue at the discretion of the investigator. For Arm D, in case CyPep-1 treatment is delayed for > 3 weeks (first 3 injections), the investigator and the Medical Monitor must assess on a case by case basis the decision whether the subject should be discontinued from the trial. Treatment delay due to TEAEs will be considered for treatment discontinuation.

For any subject who is withdrawn or discontinued from the trial, the reason, date and subsequent planned replacement therapy (if applicable), must be recorded in the electronic case report form (eCRF) and in the medical record. (S)AEs ongoing at trial withdrawal will be followed up for outcome information until resolution or stabilization (see Section 7.2.1).

When a subject is withdrawn or discontinued from active trial follow-up after having received at least one intratumoral CyPep-1 injection, and if the subject agreed on the ICF, every effort will be made to report serious adverse events (SAEs) until at least 3 months after the last intra-tumoral CyPep-1 injection administered for both trial phases.

If a subject withdraws consent from specific assessment(s) following intratumoral CyPep-1 injection (i.e. tumor biopsy, radiological or hematological assessments, etc.), all other assessments should be completed as per protocol and a protocol deviation should be recorded for both trial phases.

If a subject is withdrawn or discontinued from the trial, all data collected until the time of withdrawal will be used in the analyses.

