Hyperthyroidism	Grade 2	Continue	Treat with nonselective beta-blockers (eg, propranolol) or thionamides as appropriate	Monitor for signs and symptoms of thyroid disorders
	Grade 3 or 4	Withhold or permanently discontinue ^d		
Hypothyroidism	Grade 2, 3 or 4	Continue	Initiate thyroid replacement hormones (eg, levothyroxine or	Monitor for signs and symptoms of thyroid disorders

			liothyronine) per standard of care	
Nephritis: grading according to increased creatinine or acute kidney injury	Grade 2	Withhold	Administer corticosteroids (prednisone 1 to 2 mg/kg or equivalent) followed by taper	Monitor changes of renal function
	Grade 3 or 4	Permanently discontinue		
Neurological Toxicities	Grade 2	Withhold	Based on severity of AE administer corticosteroids	Ensure adequate evaluation to confirm etiology and/or exclude other causes
	Grade 3 or 4	Permanently discontinue		
Myocarditis	Grade 2, 3 or 4	Permanently discontinue	Based on severity of AE administer corticosteroids	Ensure adequate evaluation to confirm etiology and/or exclude other causes
Exfoliative Dermatologic Conditions	Suspected SJS, TEN, or DRESS	Withhold	Based on severity of AE administer corticosteroids	Ensure adequate evaluation to confirm etiology or exclude other causes
	Confirmed SJS, TEN, or DRESS	Permanently discontinue		
All Other irAEs	Persistent Grade 2	Withhold	Based on severity of AE administer corticosteroids	Ensure adequate evaluation to confirm etiology or exclude other causes
	Grade 3	Withhold or discontinue based on the event ^e		
	Recurrent Grade 3 or Grade 4	Permanently discontinue		

AE(s)=adverse event(s); ALT= alanine aminotransferase; AST=aspartate aminotransferase; CTCAE=Common Terminology Criteria for Adverse Events; DRESS=Drug Rash with Eosinophilia and Systemic Symptom; GI=gastrointestinal; IO=immuno-oncology; ir=immune related; IV=intravenous; SJS=Stevens-Johnson Syndrome; T1DM=type 1 diabetes mellitus; TEN=Toxic Epidermal Necrolysis; ULN=upper limit of normal.

Note: Non-irAE will be managed as appropriate, following clinical practice recommendations.

^a AST/ALT: >3.0 to 5.0 x ULN if baseline normal; >3.0 to 5.0 x baseline, if baseline abnormal; bilirubin:>1.5 to 3.0 x ULN if baseline normal; >1.5 to 3.0 x baseline if baseline abnormal

^b AST/ALT: >5.0 to 20.0 x ULN, if baseline normal; >5.0 to 20.0 x baseline, if baseline abnormal; bilirubin:>3.0 to 10.0 x ULN if baseline normal; >3.0 to 10.0 x baseline if baseline abnormal

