^c AST/ALT: >20.0 x ULN, if baseline normal; >20.0 x baseline, if baseline abnormal; bilirubin: >10.0 x ULN if baseline normal; >10.0 x baseline if baseline abnormal

^d The decision to withhold or permanently discontinue pembrolizumab is at the discretion of the investigator or treating physician. If control achieved or ≤ Grade 2, pembrolizumab may be resumed.

^e Events that require discontinuation include but are not limited to: encephalitis and other clinically important irAEs (eg. vasculitis and sclerosing cholangitis).

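### Section 1.9.3 lets pembrolizumab be withheld and, by implication, resumed after Grade 3-4 myocarditis, encephalitis or Guillain-Barre syndrome; Table 3 in 5.3.6.2, which governs, requires permanent discontinuation in at least 5 of those 6 event-grade combinations

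*Protocol*

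**What the plan says.** Protocol Section 1.9.3 lists three measures for pembrolizumab toxicity in Arm B. The first covers suspected Stevens-Johnson syndrome or toxic epidermal necrolysis: withhold until Grade 0-1, and stop for good if recovery, or a steroid taper to 10 mg prednisone per day or less, is not reached within 12 weeks. The second covers the confirmed condition: stop for good. The third is the bullet at issue: "Grade 3 or 4 myocarditis, encephalitis, or Guillain-Barre syndrome: withhold until recovery to Grades 0-1 or, if above conditions apply, permanently discontinue".

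Table 3 in Section 5.3.6.2 gives the action by event and grade:

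- Myocarditis: "Myocarditis Grade 2, 3 or 4 Permanently discontinue".
- Neurological Toxicities row, second line: "Grade 3 or 4 Permanently discontinue".
- All Other irAEs row: Grade 4 or recurrent Grade 3 is permanent discontinuation. Grade 3 is withhold or discontinue according to the event, with footnote e attached: "Events that require discontinuation include but are not limited to: encephalitis and other clinically important irAEs".

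On precedence, the lead-in to the 1.9.3 list calls its measures recommended and sends the reader to 5.3.6.2 and 5.3.6.3 for the full list. The section closes with "Related dose modification rules for CyPep-1 and pembrolizumab is detailed in" Section 5.3.6. Footnote 29 to the Schedule of Assessments says "See Section 5.3.6.2 for dose modifications and toxicity management". Section 4.3.1 counts as a reason to stop treatment any related toxicity "specified as a reason for permanent discontinuation as defined in the guidelines for dose modification due to AEs in Section 5.3.6". The Synopsis, under its dose-modification criteria, also refers pembrolizumab changes in Arm B to Section 5.3.6.

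**The concern.** The protocol gives two different actions for the same serious immune-related events, and the one in the risk-management section is the less protective. Under the bullet, permanent discontinuation is conditional; under Table 3 it is immediate and final for most of the events named. An Arm B subject who returned to Grade 0-1 and tapered steroids within 12 weeks could receive at least one more 400 mg dose under the bullet and none under Table 3. The same doubt would carry into continued access (Section 5.9.1), which ends when a discontinuation criterion is met.

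Nothing alerts a reader that the third bullet is the odd one out. The first two agree with Table 3 on withholding versus stopping; for the confirmed skin reaction, Table 3 has "Confirmed SJS, TEN, or DRESS Permanently discontinue".

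**Working it through.** There is no planned figure to reproduce. The check sets the two rules side by side for each event and grade in the bullet: 3 events x 2 grades = 6 combinations.

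| Event | Grade | Section 1.9.3 bullet | Table 3 | Conflict |
|---|---|---|---|---|
| Myocarditis | 3 | Withhold, stop only on condition | Stop for good (own row) | Firm, by name |
| Myocarditis | 4 | Same | Stop for good (own row) | Firm, by name |
| Encephalitis | 3 | Same | Stop under the neurological row; also stop under All Other irAEs through footnote e | Firm, either row |
| Encephalitis | 4 | Same | Stop for good under either row | Firm, either row |
| Guillain-Barre syndrome | 4 | Same | Stop for good under either row | Firm, either row |
| Guillain-Barre syndrome | 3 | Same | Stop for good under the neurological row; withhold or discontinue by event under All Other irAEs | Depends on classification |

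Firm conflicts: 2 (myocarditis) + 2 (encephalitis) + 1 (Guillain-Barre syndrome, Grade 4) = 5 of 6. The sixth joins them if Guillain-Barre syndrome is classed as a neurological toxicity.

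Could anything in Table 3 reconcile the two rules? Footnote d allows pembrolizumab to be resumed once control or Grade 2 or lower is reached, but it is attached only to the type 1 diabetes/hyperglycemia, hypophysitis and hyperthyroidism rows. It does not reach the three events here.

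Is there a conflict at Grade 2? No. The bullet does not mention Grade 2 myocarditis, so Table 3 applies unopposed.

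Does the choice of rule reach the statistics?

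- Treatment-limiting toxicity (Section 3.1.2): a related Grade 3 or 4 nonhematologic event in Cycle 1 qualifies under criterion 1 or 3. None of the three events is among the exceptions in criterion 3, which concern fatigue, gastrointestinal symptoms and rash. TLT status is therefore the same under both rules, and so is the Arm B rule on the first 3 or 6 subjects.
- SAP Section 11.1.3: the adverse-event overview counts events leading to pembrolizumab discontinuation and to interruption separately. A subject with such an event could move from one line to the other. These tables are descriptive.
- Analysis sets (SAP Section 7.2): membership does not depend on pembrolizumab being stopped.

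**The case against.** The strongest reply is that the protocol already settles precedence. The bullet sits in the introductory section under a lead-in that only recommends, while the Synopsis, Section 4.3.1, Schedule footnote 29 and 1.9.3 itself all point to Section 5.3.6. A site that follows any of these pointers reaches the stricter rule. Treatment also ends for unacceptable toxicity, a separate though undefined stop. This stands as a limit on the risk. It does not remove the inconsistency: directing the reader to a fuller list tells them that Table 3 says more, not that a bullet printed here is wrong.

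A second reply concerns the reference to conditions above. The bullet immediately above deals with confirmed skin reactions, so one could read the third as withhold while suspected and stop once confirmed, which would shrink the conflict. That reading is possible but less natural: the third bullet draws no line between suspected and confirmed, and the only stated conditions are the 12-week limits in the first. It is also true that the bullet never says restart; resumption is implied by withholding until recovery.

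A third reply is that Table 3 does not name Guillain-Barre syndrome, and that its only mention of encephalitis is in a footnote to the All Other irAEs row, so neurological events are not all routed cleanly through the neurological row. This is correct. A reader might infer that all six combinations conflict outright; the table supports five without a classification step.

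**Conclusion.** The inconsistency is real and worth correcting. It is firm for 5 of the 6 event-grade combinations and depends on classification for Grade 3 Guillain-Barre syndrome. It rests on reading the conditions as the 12-week limits and on taking resumption as implied. The general-instructions heading of Table 3 has no text in the copy available, so the conclusion uses only the event rows and footnotes.

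The consequence is an Arm B safety matter for a reader who acts on the bullet alone. Two stronger inferences are not supported. One is that a subject might receive a large number of further doses, up to most of the 18 allowed. That figure would need an assumed event date, restart date and time without progression, and Section 4.3.1 counts administrations, so even the effect of a missed slot is not fixed. The documents support only at least one dose against none, and they give no incidence from which to state a probability. The other is that trial results are affected: no estimate, decision rule or analysis set changes.

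**What to change.** Delete the third bullet in Section 1.9.3. Alternatively, replace it with: *Grade 2, 3 or 4 myocarditis, or Grade 3 or 4 encephalitis, Guillain-Barre syndrome or other neurological toxicity: permanently discontinue pembrolizumab.* This wording also settles the classification of Guillain-Barre syndrome. In either case, add a sentence to 1.9.3 saying that Table 3 in Section 5.3.6.2 governs pembrolizumab actions for immune-related events.

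The cost is a short text change made under Sections 10.6 and 11.1, in both protocol versions (10.0 and 10.1) if they share the wording. It can be bundled with the next amendment. The SAP and data collection are untouched. Section 5.6.3 places Table 3 in 5.3.6.3 rather than 5.3.6.2; that is a separate clerical correction.
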